### ***Analysis of pre-treatment and post-treatment adverse events***

- All pre-treatment AEs by primary SOC and PT, sorted by the internationally agreed SOC order and decreasing incidence of PTs (in the alirocumab group) within each SOC;
- All pre-treatment AEs leading to treatment discontinuation by primary SOC and PT, sorted by the sorting order defined above;
- All post-treatment AEs by primary SOC and PT, sorted by the internationally agreed SOC order and decreasing incidence of PTs (in the alirocumab group) within each SOC;
- All post-treatment SAEs by primary SOC and PT, sorted by the sorting order defined above.

### ***Subgroup of patients with 2 consecutive LDL-C <25 mg/dL (<0.65 mmol/L)***

If applicable, similar summaries of TEAEs as those described above will be also provided on the safety subgroup population of patients with 2 consecutive results of calculated LDL-C <25 mg/dL (<0.65 mmol/L, as defined in [Section 2.1.5](#)) in both treatment groups. Only TEAE for which it will be confirmed or unclear that they occurred, worsened or became serious the day or after the first level of LDL-C <25 mg/dL (<0.65 mmol/L) will be considered.

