11.4.4 Analyses of other endpoints

All analyses for other endpoints will be performed on the Safety population. The baseline value is defined as the last available value before first double-blind IMP (injection or capsule, whichever comes first).

The number and percentage of patients with 2 consecutive results, spaced out by at least 21 days, of calculated LDL-C <25 mg/dL and calculated LDL-C <15 mg/dL, respectively, will be provided by treatment group.

The antibody status (positive/negative) and antibody titers will be summarized by treatment group and visit using descriptive statistics. If appropriate, correlations between antibody titers, safety and/or efficacy endpoints will be provided by graphical methods.

HbA1_c will be summarized by time points using number of available data, mean, SD, median, minimum, and maximum for each treatment group. The time profile of each parameter will be also plotted by treatment group with the corresponding SE.

Further details will be provided in SAP.

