### ***Observation period***

The period of safety observation starts from the time when the patient gives informed consent and is divided into the following periods:

- The PRE-TREATMENT period: defined as the time from the signed informed consent up to the first dose of double-blind IMP;
- The treatment-emergent adverse event (TEAE) period: defined as the time from the first dose of double-blind IMP up to the day of last dose of double-blind IMP injection+70 days (10 weeks) as residual effect of alirocumab is possible until 10 weeks after the discontinuation of double-blind IMP injection.

The TEAE period will include:

- The TREATMENT period defined as the time from the first dose of double-blind IMP up to the day of last dose of double-blind IMP injection + 21 days, as serum concentration of alirocumab is expected to be  $>10 \mu\text{g/mL}$  for approximately 21 days following administration of 150 mg, and because throughout the previous studies it was observed that when alirocumab concentrations declined below this concentration, decrease in effect on LDL-C is observed.
- The RESIDUAL TREATMENT defined as the time from the day of last dose of double-blind IMP injection + 22 days up to the day of last dose of double-blind IMP injection + 70 days (10 weeks).
- The POST-TREATMENT period: defined as the time starting the day after the end of the TEAE period (ie, 71 days after the day of last dose of double-blind IMP injection).

The on-study observation period is defined as the time from the day of first dose of double-blind IMP (capsule or injection, whichever comes first) until the last protocol planned visit of the patient. The last protocol planned visit is defined as the follow-up visit if done, or else 32 weeks after the randomization of the patient.

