### **2.1.5 *Other endpoints***

The assessment endpoint listed below is defined using the same definitions and rules as for calculated LDL-C, when applicable (see [Section 2.1.3.1](#)).

- The absolute change in HbA1c (%) from baseline to Week 12 and Week 24. PCSA criteria for HbA1c will be used (see [Appendix A](#)).
- The proportion of patients with 2 consecutive results, spaced out by at least 21 days, of calculated LDL-C <25 mg/dL (<0.65 mmol/L) (respectively calculated LDL-C <15 mg/dL, ie, <0.39 mmol/L) during the treatment period and the time to the first calculated LDL-C <25 mg/dL (respectively, calculated LDL-C <15 mg/dL for these patients).

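### In the low-LDL-C safety subgroup, adverse events count from the first LDL-C <25 mg/dL but entry needs a second value at least 21 days later, so deaths and some early discontinuations drop out with the patient

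*SAP*

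**What the plan says.** SAP 2.4.5.1 plans, if applicable, to repeat the TEAE summaries in the "safety subgroup population of patients with 2 consecutive results of calculated LDL-C <25 mg/dL", in both arms. The summaries being repeated include serious TEAEs, TEAEs leading to death and TEAEs leading to permanent treatment discontinuation. Only events that "occurred, worsened or became serious the day or after the first level of LDL-C <25 mg/dL" are counted, or events whose timing is unclear.

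For membership the subsection refers to SAP 2.1.5, which defines "The proportion of patients with 2 consecutive results, spaced out by at least 21 days, of calculated LDL-C <25 mg/dL" and places those results "during the treatment period and the time to the first calculated LDL-C <25 mg/dL". SAP 2.1.4 (Observation period) defines the treatment period as "the time from the first dose of double-blind IMP up to the day of last dose of double-blind IMP injection + 21 days".

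Protocol 11.4.4 has the same spacing rule ("patients with 2 consecutive results, spaced out by at least 21 days") but does not state that the values must fall in the treatment period. Neither document gives a landmark rule, a single-value set or a sensitivity analysis for this subgroup.

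**The concern.** The clock starts at the first low value, while membership is settled only by a later one. Between the two, a patient can be removed by the very outcome being tabulated. A death leaves no second sample. A discontinuation brings the end of the treatment period forward and may leave no qualifying sample. This is immortal-time bias. In the discontinuation and death rows it can only lower the subgroup proportion.

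This subgroup is the planned look at whether very low LDL-C is harmful. Protocol Section 4 reports no safety signal in earlier pooled studies for patients with at least two consecutive values below 25 or 15 mg/dL, and commits to further monitoring of adverse events associated with low LDL-C. A reader will use this trial's tables for the same purpose.

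**Working it through.** There is no stated figure to reproduce, so the check is date arithmetic.

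**Inputs.**
- Scheduled LDL-C on Days 29, 57, 85, 113 and 169, and none at follow-up (Protocol 1.2 and 9.1.3.1).
- Injections every 14 days from Day 1 to Day 155 (Protocol 6.1), given after sampling on visit days (Protocol 8.1.2).
- Early visit within 5 days of stopping, if possible (Protocol 10.3.4).
- Treatment period to last injection + 21 days; TEAE period to last injection + 70 days (SAP 2.1.4).

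**Entry rule.** With the first low value on day a and the second on day b, entry needs b ≥ a + 21 and b ≤ last injection + 21.

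**Example.** First low value on Day 29, injection that day, event on Day 36, drug stopped. The treatment period ends on Day 29 + 21 = 50. The early visit falls by Day 36 + 5 = 41, only 12 days after the first value. The next scheduled sample, Day 57, is outside the period. The patient is not in the subgroup and the event is in none of its tables.

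**Blocked stop days.** For each stop day from the first low value to Day 168, assume nominal dates, LDL-C staying below 25 mg/dL and an early visit at stop + 5:
- Weeks 4, 8 and 12: a stop before the next injection (14 days) ends the period at a + 21, the next visit is at a + 28, and the early visit is at most a + 18. These stops are blocked. After the next injection the period runs to a + 35, so the visit at a + 28 qualifies.
- Week 16: a sample on or after Day 134 is needed. The early visit reaches that day only for stops from Day 129, so Days 113 to 128 (16 days) are blocked. With no early visit, Day 169 must fall within last injection + 21. Only the Day 155 injection allows this, so Days 113 to 154 (42 days) are blocked.

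**Effect on the discontinuation proportion.** Assume a constant hazard giving 5% per 24 weeks: λ = −ln(0.95)/168 = 0.000305 per day. With D days to Day 168 and B blocked days, true T = 1 − exp(−λD), missed M = 1 − exp(−λB), and reported R = (T − M)/(1 − M).

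| First low value | B of D | T | M | R | R/T |
|---|---|---|---|---|---|
| Week 4 | 14 of 140 (10%) | 4.18% | 0.43% | 3.77% | 0.90 |
| Week 8 | 14 of 112 (12.5%) | 3.36% | 0.43% | 2.95% | 0.88 |
| Week 12 | 14 of 84 (17%) | 2.53% | 0.43% | 2.11% | 0.84 |
| Week 16 | 16 of 56 (29%) | 1.70% | 0.49% | 1.21% | 0.72 |
| Week 16, no early visit | 42 of 56 (75%) | 1.70% | 1.27% | 0.43% | 0.25 |

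**Deaths.** A death within 21 days of the first low value always prevents entry. On scheduled samples this extends to 28 days, or 56 days after Week 16. For a completer the TEAE period ends on Day 155 + 70 = 225, so the uncovered share is 28/196 (14%), 28/168 (17%), 28/140 (20%) and 56/112 (50%) for a first low value at Weeks 4, 8, 12 and 16.

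**The case against.** **Stopping does not exclude automatically.** A reader might infer that the gap between the two values is guaranteed free of any event that ends treatment. The documents support that only for death. At Weeks 4 to 12 a stop is blocked in 14 of the 28 gap days, and at Week 16 in 16 of 56 when the early visit takes place. A patient who stops after the Day 43 injection is on treatment to Day 64, so the Day 57 sample counts.

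**Visit timing matters.** The Week 8 window is ±7 days. A sample on Day 50 is exactly 21 days after Day 29 and on the last day of the period, which brings the 14 blocked days for a Week 4 first value to zero. Unscheduled samples also count (SAP 2.5.5). Stops for reasons other than adverse events exclude in the same way.

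**Nothing is lost from the report.** A reader might infer that these events disappear. They remain in the full safety-population tables of TEAEs, discontinuations and deaths (SAP 2.4.5.1 and 2.4.5.2). Those tables do not link them to low LDL-C. The subgroup analysis is descriptive, with no formal testing.

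**The numbers are small.** At the assumed rate, about 0.4 to 0.5 discontinuations per 100 low-LDL-C patients are missed. If 20 to 120 patients entered the subgroup (an assumption), that is about 0.1 to 0.6 patients. Protocol Section 4 expects few patients below 25 mg/dL, although it also reports a substantial number in earlier studies.

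**The two-value rule has a purpose.** It is in the protocol and identifies sustained low LDL-C.

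All of this stands as a limit on size. None of it removes the mismatch between entry and the start of counting, or changes its direction for discontinuations and deaths.

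**Conclusion.** The mismatch is in the SAP text and no other section corrects it. Death before the second sample always removes patient and event from the subgroup; stopping injections soon after the first low value may. The reported subgroup proportion of discontinuations is about 0.90 to 0.72 of the true one. This rests on nominal visits, sustained low LDL-C, an attended early visit and an assumed 5% per 24 weeks, which is not a figure from the documents. The absolute shortfall is small.

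The larger figures (75% of stop days blocked, 50% of the TEAE window uncovered for deaths) belong to a first low value at Week 16, and the 75% also needs the early visit to be missed. They should not be read as the general size. Part of the discontinuation effect comes from the treatment-period limit in SAP 2.1.5, which Protocol 11.4.4 does not state; the exclusion of deaths comes from the two-value rule itself. Whether the first level means the first ever or the first of the qualifying pair makes no difference, since either precedes entry by at least 21 days. No alpha or power is affected. This is a cheap improvement to a stated safety analysis and does not put the trial's conclusions in doubt.

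**What to change.** In SAP 2.4.5.1, keep the two-value tables as planned. Add the same TEAE tables for all patients with at least one calculated LDL-C below 25 mg/dL during the treatment period, counting TEAEs from the day of that value. State that conclusions on discontinuations and deaths at low LDL-C rest on this single-value set.

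The cost is one extra set of descriptive tables and a sentence or two in the SAP, with no new data. The downside is that the set includes some patients with a transient low value, and those first low at Week 24, who have no later scheduled sample. Showing both sets side by side deals with this.

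Moving the start of the two-value count to the second value should not be the remedy. It would align the clock with entry, but it recovers no excluded patient and drops the events between the two values in patients who do qualify, which is 14% to 50% of a completer's counting window by the shares above.

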#### **2.4.5.2 Deaths**

The following summaries of deaths will be generated for the safety population.

- Number (%) of patients from the safety population who died by study period (on-study, on-treatment, post-study) and reasons for death as adjudicated by the clinical events classification (CEC);
- Deaths in nonrandomized patients or randomized but not treated patients;
- TEAEs leading to death (death as an outcome on the adverse event case report form page as reported by the Investigator) by primary SOC, HLT, and PT showing number (%) of patients sorted by internationally agreed SOC order, with HLT, and PT presented in alphabetical order within each SOC. TEAE leading to death are TEAE that led to death regardless of timing of death in relation to IMP injection (ie, death occurring in the TEAE period or during the post-treatment period).

#### **2.4.5.3 Analyses of laboratory variables**

The summary statistics (including number, mean, median, first quartile (Q1), third quartile (Q3), standard deviation, minimum and maximum) of all laboratory variables (central laboratory values and changes from baseline) will be calculated for each visit or study assessment (baseline, each post-baseline time point, last on-treatment, worst on-treatment value) by treatment group. In addition, for some parameters of interest, mean changes from baseline with the corresponding SE could be plotted over time (at same time points) in each treatment group. This section will be organized by biological function as specified in [Section 2.1.4.3](#). For glucose, only fasting samples will be summarized.

The incidence of PCSAs (list provided in [Appendix A](#)), at any time during the TEAE period will be summarized by biological function and treatment group whatever the baseline level and/or according to the following baseline status categories:

- Normal/missing;
- Abnormal according to PCSA criterion or criteria.

Glucose (quantitative summary and PCSA) will also be analyzed, overall and according to the diabetic status at baseline.

For parameters for which no PCSA criteria are defined, similar table(s) using the normal range will be provided.

If any clinically significant signal is detected and need further characterization, exploration of time to onset will be performed for selected PCSAs assessed during the TEAE period as described below to account for the differential exposure time in all patients.

Kaplan-Meier curves during TEAE period will be also provided using the midpoint of the time interval between the first assessment with PCSA and the previous assessment. Only the first event (PCSA) will be counted. Patients without any event will be censored at the last assessment performed during the TEAE period.

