 - ii) Documented previous ischemic stroke with a focal ischemic neurological deficit that persisted more than 24 hours, considered as being of atherothrombotic origin. CT or MRI must have been performed to rule out primary hemorrhage and non-ischemic neurological disease.
 - iii) Documented chronic kidney disease (CKD) as defined by $30 \leq \text{eGFR} < 60 \text{ mL/min/1.73 m}^2$ for 3 months or more, including the screening visit
 - iv) Known history of diabetes mellitus AND 2 or more additional risk factors (as listed below):
 - (a) History of hypertension (established on antihypertensive medication)
 - (b) Documented history of ankle-brachial index ≤ 0.90
 - (c) Documented history of microalbuminuria or macroalbuminuria ([44](#)) OR dipstick urinalysis at screening visit (Week -3) with $>2 +$ protein
 - (d) Documented history of preproliferative or proliferative retinopathy or laser treatment for retinopathy
 - (e) Known family history of premature CHD (CHD in father or brother before 55 years of age; CHD in mother or sister before 65 years of age)

I 02. Signed written informed consent

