##### ***General common rules***

All safety analyses will be performed on the safety population as defined in [Section 2.3.2](#), unless otherwise specified, using the following common rules:

- Safety data in patients who do not belong to the safety population (eg, exposed but not randomized) will be listed separately;
- The baseline value is defined as the last available value obtained up to the date and time of the first double-blind IMP administration (capsule or injection, whichever comes first), except otherwise specified.
- The potentially clinical significant abnormality (PCSA) values are defined as abnormal values considered medically important by the Sponsor according to predefined criteria/thresholds based on literature review and defined by the Sponsor for clinical laboratory tests and vital signs (PCSA version dated January 2009 [[Appendix A](#)]). In case the threshold defined in the PCSA list for a given lab parameter is below the ULN, the following PCSA criterion will be used for the PCSA analysis: >PCSA threshold or > ULN (if  $ULN \geq PCSA$  threshold).
- PCSA criteria will determine which patients had at least 1 PCSA during the TEAE period, taking into account all evaluations performed during TEAE period, including nonscheduled or repeated evaluations.
- The treatment-emergent PCSA denominator by group for a given parameter will be based on the number of patients assessed for that given parameter at least once during the TEAE period.

All measurements, scheduled or unscheduled, fasting or not fasting, will be assigned to analysis windows defined in [Section 2.5.4, Table 2](#) in order to provide an assessment for Week 4 to Week 24 time points.

- For quantitative safety parameters based on central laboratory/reading measurements, descriptive statistics will be used to summarize results and change from baseline values by visit and treatment group using analysis windows. Summaries will also include the last on-treatment value and the worst on-treatment value. The last on-treatment value is defined as the last value collected during the treatment period (see [Section 2.1.4](#)). The worst on-

treatment value is defined as the nadir and /or the peak value during the treatment period according to the direction (minimum or maximum) of the abnormality as defined in the PCSA list.

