### ***Analysis of all treatment-emergent adverse events***

The following treatment-emergent adverse event summaries will be generated for the safety population.

- Overview of TEAEs, summarizing number (%) of patients with any
  - TEAE;
  - Serious TEAE;
  - TEAE leading to death;
  - TEAE leading to permanent treatment discontinuation;
- All TEAEs by primary SOC, HLGT, HLT, and PT, showing number (%) of patients with at least 1 TEAE sorted by the SOC internationally agreed order. The other levels (HLGT, HLT, PT) will be presented in alphabetical order;
- All TEAEs by primary SOC and PT, showing the number (%) of patients with at least 1 TEAE, sorted by the internationally agreed SOC order and by decreasing incidence of PTs within each SOC. This sorting order will be applied to all other tables, unless otherwise specified;
- All TEAEs by treatment group regardless of relationship in one column and, in the same table a second column with TEAEs related to alirocumab according to investigator's opinion by primary SOC, HLGT, HLT, and PT, sorted by the sorting order defined above;
- All TEAEs by maximal intensity (ie, mild, moderate, or severe), presented by primary SOC and PT, sorted by the sorting order defined above;
- Kaplan-Meier curves will be provided, when appropriate, for time from first dose of double-blind IMP (capsule or injection, whichever comes first) to the first occurrence of selected TEAEs. Patients without any event will be censored at the end of the TEAE period. Selected TEAEs could be local injection site reactions, general allergic reactions, hepatic disorders, diabetes among non-diabetic patients at baseline and TEAE related to any clinically significant signal that needs further characterization.

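### The laboratory PCSA time-to-onset curves do not exclude patients who already meet the PCSA at baseline, so a persisting threshold abnormality can be plotted as an on-treatment onset

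*SAP*

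**What the plan says.** SAP 2.4.5.3 first plans PCSA incidence tables for the TEAE period, overall and/or split by baseline status (Normal/missing, or abnormal by the PCSA criterion). It then adds a conditional step. If a signal needs characterising, time to onset is explored for selected PCSAs "to account for the differential exposure time in all patients".

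Three rules define these curves:
- The event date is set "using the midpoint of the time interval between the first assessment with PCSA and the previous assessment".
- A patient contributes at most one event, the earliest.
- For everyone else the censoring rule applies: "Patients without any event will be censored at the last assessment performed during the TEAE period".

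The baseline split given for the tables is not repeated for the curves, and no at-risk set is defined. The general rules in SAP 2.4.5 fill the gap. The default analysis set is the one in SAP 2.3.2 ("All safety analyses will be performed on the safety population as defined in" that section), with room for stated exceptions. The event rule reads: "PCSA criteria will determine which patients had at least 1 PCSA during the TEAE period". Neither rule excludes anyone by baseline status.

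Elsewhere the SAP does restrict by baseline. In SAP 2.4.5.1, one candidate adverse-event curve is "diabetes among non-diabetic patients at baseline". In SAP 2.4.5.3, hepatitis C seroconversion is defined only for patients negative at baseline.

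**The concern.** Dating an onset at the midpoint between two assessments is sound only if the earlier one was free of the abnormality. Nothing in SAP 2.4.5.3 requires that. A patient who enters with a threshold abnormality and keeps it would appear as an event, dated to a day on which nothing began.

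Some baseline abnormalities follow from the entry criteria. Protocol 7.1 admits chronic kidney disease with eGFR 30 to <60, including at the screening visit, and SAP Appendix A lists that range as a PCSA category. Protocol 7.1 also admits "Known history of diabetes mellitus AND 2 or more additional risk factors", and Protocol 7.2.1 excludes poorly controlled diabetes only above an HbA1c of 9%. The fasting glucose PCSA starts at 7 mmol/L.

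The curves are drawn only once a signal is suspected. That is when new onset has to be told apart from persistence, and an undefined risk set would then be settled after the signal had been seen.

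**Working it through.** The plan states no figure for PCSA time to onset, so there is none to reproduce. The check is a reading of the rule followed by an illustration.

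**1. The rule applied to one patient.** The TEAE period starts at the first double-blind dose (SAP 2.1.4). The baseline value is the last one up to that dose (SAP 2.4.5). Chemistry and haematology are drawn at Weeks 0, 12 and 24, that is Days 1, 85 and 169 (Protocol 1.2).
- Fasting glucose is ≥7 mmol/L at Day 1 and at Day 85.
- The first PCSA within the TEAE period is at Day 85, and the previous assessment is Day 1.
- Plotted onset: (1 + 85)/2 = Day 43.
- For the liver panel the next sample is Day 29, giving (1 + 29)/2 = Day 15.

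**2. Which PCSAs can pre-exist (SAP Appendix A).**

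| PCSA | Can it be present at baseline? |
|---|---|
| eGFR 30 to <60; fasting glucose ≥7 mmol/L; uric acid >408 µmol/L; creatinine ≥150 µmol/L | Yes, fixed thresholds |
| Creatinine change ≥30% or ≥100%; haemoglobin decrease ≥20 g/L | No, defined by change from baseline |
| Vital signs (heart rate, blood pressure, weight) | No, each requires a change from baseline |
| ALT, AST, CPK >3 ULN | Rarely, excluded at screening (Protocol 7.2.1, E 32) |

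**3. Size when persistence is equal in both arms.** Let π be the proportion with the PCSA at baseline, q the probability that it is seen again on treatment, and f the new-onset risk in the others. The plotted cumulative incidence is C = πq + (1 − π)f. The risk difference is (1 − π)(f₁ − f₀). The documents give none of π, q or f, so all are assumed.

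With q = 90% and f = 10% on alirocumab versus 5% on ezetimibe:

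| π | Alirocumab | Ezetimibe | Difference (points) | Ratio |
|---|---|---|---|---|
| 0% | 10.0% | 5.0% | 5.0 | 2.0 |
| 5% | 4.5 + 9.5 = 14.0% | 4.5 + 4.75 = 9.25% | 4.75 | 1.51 |
| 15% | 13.5 + 8.5 = 22.0% | 13.5 + 4.25 = 17.75% | 4.25 | 1.24 |

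A second set uses f = 8% versus 4% (ratio 2.0, difference 4.0 points). Ranges run from q = 70% to q = 90%:

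| π | Difference (points) | Ratio | Share of plotted events that pre-existed |
|---|---|---|---|
| 5% | 3.8 | 1.52 to 1.46 | 36% to 42% |
| 10% | 3.6 | 1.34 to 1.29 | 54% to 60% |
| 20% | 3.2 | 1.19 to 1.15 | 72% to 77% |

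Example for the last column, with 400:200 patients, π = 10% and q = 70%: pre-existing 600 × 0.10 × 0.70 = 42; new 0.90 × (400 × 0.08 + 200 × 0.04) = 36; 42/78 = 54%.

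**4. Size when persistence is unequal.** Take π = 20% and f = 8% versus 4%.
- q = 90% on alirocumab, 70% on ezetimibe: (18.0 + 6.4) − (14.0 + 3.2) = 24.4 − 17.2 = 7.2 points.
- q = 70% on alirocumab, 90% on ezetimibe: (14.0 + 6.4) − (18.0 + 3.2) = 20.4 − 21.2 = −0.8 points.

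Restricting to patients without the PCSA at baseline gives 4.0 points in both cases, because π and q drop out.

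**The case against.** The best reply is that the SAP never says prevalent cases count as onsets. It calls the analysis time to onset, and a midpoint rule presupposes a clean earlier visit. The phrase about all patients describes exposure time and does not set the risk set. All of that is fair, and a careful programmer might apply the exclusion unprompted. It is still not a written rule. The event is a PCSA in the TEAE period, the default population is everyone treated, and that combination gives the Day 43 result.

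A second reply is that the separation already exists in the tables: incidence by baseline status, and glucose by diabetic status. This stands in part. The baseline split is worded and/or, so the plan does not strictly require it. It carries no timing. A diabetic patient already at 7 mmol/L or more would still be an onset within the diabetic stratum.

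Third, the comparison with the diabetes adverse-event curve is weak. That curve is one item in a list of possible curves, not a general baseline rule. This stands, and the point does not depend on it.

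Fourth, a ratio exaggerates the effect on a cumulative-incidence plot. With 15% abnormal at baseline, the absolute gap falls only from 5.0 to 4.25 points. This also stands, and both scales are given above.

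A reader might infer that every arm difference in laboratory PCSAs is diluted, or that baseline PCSAs are frequent in this trial. The documents support neither. Many PCSAs cannot pre-exist or are screened out, dilution needs equal persistence, and no prevalence is given. The diabetes-with-risk-factors route without CHD, PAD or stroke is also capped at 25% of randomised patients (Protocol section 4), although diabetics entering through CHD are not capped.

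**Conclusion.** The point holds for threshold-based laboratory PCSAs. As written, SAP 2.4.5.3 lets a persisting baseline abnormality enter the curve as an on-treatment event at a false date. Equal persistence in the two arms lowers the relative contrast and slightly narrows the absolute one. Unequal persistence can enlarge or reverse the difference.

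The size cannot be derived from the documents. The ratios of 1.15 to 1.52 against a true 2.0 rest wholly on assumed prevalence, persistence and onset rates, and at zero prevalence nothing changes.

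It is a minor point. The curves are exploratory, limited to selected PCSAs and drawn only after a signal, and SAP 2.4.5 plans no formal safety testing. It would be wrong to infer that the incidence tables, the adverse-event analyses or any efficacy result are affected.

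**What to change.** Add one sentence to SAP 2.4.5.3: *Time-to-onset curves are restricted to patients in the Normal/missing baseline category for that PCSA.* Patients abnormal at baseline stay in the incidence table by baseline status.

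The category already exists in that section, and SAP 2.5.3 already places missing baselines in it, so no new derivation is needed. The vital-sign section (SAP 2.4.5.4) uses the same curve wording but does not need the change, because its PCSAs require a change from baseline.

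The cost is a slightly smaller number at risk. At an assumed 15% abnormal at baseline, 400 × 0.85 = 340 and 200 × 0.85 = 170 patients would remain.
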